The secondary endpoints will include the mean Δ CAL from baseline at three and six months and the mean Δ CAL between study treatments at three and six months post-implantation; the LBG at six months; percent bone fill (%BF) in a vertical and horizontal direction compared to baseline and six months post-implantation, a composite endpoint combining Δ CAL and %BF; Probing Depth Reduction (PDR) from baseline at three and six months post-implantation, Change in Gingival Recession (Δ GR) from baseline at three and six months post-implantation; Wound-Healing (WH) scale and gingival wound evaluation during the first four weeks, and bleeding on probing (BOP) at three months.

Dose Selection Overview:

The goal of the feasibility study is to identify either the 0.1%, 0.3% or 0.4% active dose to be compared vs. the β -TCP control in a pivotal study, based on the observed safety and effectiveness together with past study results. No formal interim analyses are planned.

This study will not be used for labeling purposes, but will be used to plan the subsequent pivotal study. The Sponsor retains the right to pick any of the three active doses moving forward to the pivotal study.

Statistical Considerations:

The primary effectiveness endpoint is a composite endpoint that considers radiographic and clinical measurements at six months post-implantation: the amount of linear bone growth (LBG), which is assessed with the use of radiographs, and the change from baseline of clinical attachment level (Δ CAL), which is calculated from clinical assessments. To be a success, Δ CAL ($CAL_{6\text{ mo}} - CAL_{\text{Baseline}}$) must be at least -1.5 mm and a minimum measurement of 1 mm is required for linear bone growth (LBG) measured from baseline; both must be met at 6 months to define a primary effectiveness success for the tooth (Lynch S, Lavin P *et al. J Periodontal* 2006;77:1314). The number of teeth that meet the success criteria for the primary endpoint will be compared between the study treatments. The components of the primary effectiveness outcome, including LBG in particular, are also of interest.

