12.1.1 Hypothesis Testing

As this is a feasibility study, formal hypothesis tests for the purposes of regulatory approval or labeling claims will not be performed. Nonetheless, for internal purposes, statistical hypothesis tests may be performed as follows.

A two-sided superiority hypothesis test follows for the composite success percent endpoint:

$$\begin{aligned} H_0: p_G - p_C &= 0, \text{ versus} \\ H_a: p_G - p_C &\neq 0 \end{aligned}$$

where p_G and p_C are the respective percents of subjects achieving success as specified above for [REDACTED] GFeBGS and Active control treatment groups. This hypothesis testing format will be used for the other effectiveness endpoints measured as success outcomes.

The two-sided superiority hypothesis test is the following for the continuous and percent based measures relative to baseline:

$$\begin{aligned} H_0: \Delta_G - \Delta_C &= 0, \text{ versus} \\ H_a: \Delta_G - \Delta_C &\neq 0 \end{aligned}$$

where Δ_G and Δ_C are the respective mean changes in outcomes relative to baseline for [REDACTED] GFeBGS and Active control treatment groups. The same hypothesis testing format will be used for other continuous effectiveness endpoints.

For each primary and secondary effectiveness endpoint, an alpha level of 0.05 will be used.

CONFIDENTIAL

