12.1.10 Dose Selection

Dose selection for future study will be based on an analysis of the primary composite endpoint. Five different dose response patterns will be examined and modeled statistically, with the dose selected based on the best model fit. Specifically, we will perform a logistic regression of the primary composite endpoint and apply linear contrasts to the model according to the following five dose response patterns for success:

1. An increase in a linear manner from the Treatment I to Treatment IV groups
2. A plateau in the Treatment II group, with similar performance in groups II through IV
3. A plateau in the Treatment III group, with similar performance in group IV
4. An apex in the Treatment III group; best performance in group III, lower performance in the other groups
5. An apex in the Treatment IV group; best performance in group IV, lower performance in the other groups

For each contrast, the Wald test statistic will be computed and the pattern that corresponds to the largest value of the Wald statistic will be considered the best fit and guide the selection of the optimal dose.

For patterns where there is insufficient data to distinguish between effective doses, patterns 2 and 3 for example, the 0.3% rh-bFGF dose may be selected based on prior data and pre-clinical testing.

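### Section 12.1.10 ranks directional dose-response patterns by a Wald statistic whose sign is not fixed, so in chi-square form an apex pattern can win because its arm is the worst

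*Protocol*

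**What the plan says.** Section 12.1.10 bases dose selection on a logistic regression of the primary composite. It will "apply linear contrasts to the model according to the following five dose response patterns for success". All five patterns carry a direction: a linear rise, a plateau from Treatment II, a plateau from Treatment III, and two apex patterns, "An apex in the Treatment III group; best performance in group III, lower performance in the other groups" and "An apex in the Treatment IV group; best performance in group IV, lower performance in the other groups".

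The ranking step is that "the pattern that corresponds to the largest value of the Wald statistic will be considered the best fit", and the winner is to "guide the selection of the optimal dose". The section prints no coefficients, does not name the form of the Wald statistic, and sets no condition on the sign of the contrast.

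Two passages soften the rule. The fallback in the same section begins "For patterns where there is insufficient data to distinguish between effective doses, patterns 2 and 3 for example" and allows 0.3% to be chosen in that case. The Dose Selection Overview in Section 1.0 states: "The Sponsor retains the right to pick any of the three active doses moving forward to the pivotal study".

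**The concern.** The patterns have a direction, but the criterion that ranks them need not have one. The Wald test of a contrast in logistic regression is commonly reported as a chi-square, the square of estimate over standard error. Squaring removes the sign. If one arm is uniquely poor, its apex contrast is strongly negative and its chi-square is large, so the rule would call an apex at that arm the best fit.

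The primary objective is to obtain dosing data that guide the dose for future study. Two analysts who follow the same sentence, one ranking signed z and the other ranking chi-squares, can name different doses from the same data. One of those doses may be the arm with the lowest success rate.

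**Working it through.** **The protocol's own figure.** The dose rule states no number. The sample size in Section 12.1.2, which sets 20 per arm, does reproduce. The standard error is sqrt((1.20² + 2.30²)/20) = 0.580, the noncentrality is 1.70/0.580 = 2.93 and the Welch df is 28.6. Power is 0.808, against at least 80% stated. 80/0.85 = 94.1, against 94 stated. The point does not rest on sample size.

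**Inputs and assumptions.**
- 20 evaluable subjects per arm (Section 12.1.2).
- Arms numbered as in Section 5.1: I control, II 0.1%, III 0.3%, IV 0.4%. Section 7.1.1.1 numbers them differently, with control as IV, so the numbering that the patterns rely on must be reconciled.
- Logistic model with treatment arm only.
- Contrast coefficients assumed: (-3,-1,1,3), (-3,1,1,1), (-1,-1,1,1), (-1,-1,3,-1), (-1,-1,-1,3).
- Success counts and true success rates assumed.

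**Formula.** For x successes of 20, the arm log-odds is L = ln(x/(20-x)) with variance v = 1/x + 1/(20-x). For contrast c, z = Σ cL / sqrt(Σ c²v) and chi-square = z².

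**Example with 11, 14, 15 and 6 successes.** L = 0.2007, 0.8473, 1.0986, -0.8473. v = 0.2020, 0.2381, 0.2667, 0.2381.
- Pattern 5: estimate = 3(-0.8473) - (0.2007 + 0.8473 + 1.0986) = -4.688. Variance = 0.2020 + 0.2381 + 0.2667 + 9(0.2381) = 2.850, SE 1.688. z = -2.78.
- Pattern 4: estimate = 3(1.0986) - (0.2007 + 0.8473 - 0.8473) = 3.095. Variance = 0.2020 + 0.2381 + 9(0.2667) + 0.2381 = 3.078, SE 1.754. z = +1.76.

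| Pattern | z | Chi-square |
|---|---|---|
| 1 linear rise | -1.37 | 1.87 |
| 2 plateau from II | +0.31 | 0.10 |
| 3 plateau from III | -0.82 | 0.67 |
| 4 apex III | +1.76 | 3.11 |
| 5 apex IV | -2.78 | 7.71 |

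The largest chi-square belongs to pattern 5, although arm IV has 6/20 = 30% success against 11/20 = 55% on control. The largest signed z belongs to pattern 4, whose apex is the observed best arm (15/20 = 75%).

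**Sensitivity to coefficients.** With 12, 12, 4 and 12 successes, pattern 4 has the largest chi-square (8.41, z = -2.90) although arm III is the worst. With 12, 12, 12 and 4, pattern 5 has it (8.41, z = -2.90). Both winners are unchanged under two other coefficient sets, one with dose-scaled linear and ramped plateau contrasts and one with an umbrella-shaped apex at III.

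**How often.** The chi-square form was applied to 200,000 simulated trials per scenario with 20 per arm. The few trials with an arm at 0 or 20 successes were excluded (about 0.2% at most). The table gives the share in which pattern 4 or 5 wins with a negative contrast. In essentially all of these the named arm is lowest or tied lowest.

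| Assumed true success, control/0.1%/0.3%/0.4% | False apex |
|---|---|
| 40/55/70/70% | about 1% |
| 50/70/70/70% | about 8% |
| 50/60/65/65% | about 10% |
| 50/50/50/50% | about 23% |
| 50/65/65/50% | about 31% |
| 40/70/70/40% | about 36% |

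**The case against.** **A literal reading may avoid the error.** If the statistic is a signed z with coefficients oriented to each pattern, the largest value in the example is pattern 4 and nothing goes wrong. This stands as a limit: the fault needs the chi-square or absolute-value reading. The text does not choose between them, and the chi-square is a usual form.

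**The patterns already state a direction.** Data in which IV is worst do not fit an apex at IV as worded, and an attentive analyst would notice. That is so, but the ranking sentence equates best fit with the largest statistic and never checks direction. Sections 12.1.8 and 12.1.9 do fix direction, through lower bounds for GFeBGS minus control. The two-sided test in Section 12.1.1 concerns each dose against control and does not say how contrasts are ranked.

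**Coefficients and test form belong in the SAP.** Coefficients may well sit there. The ranking criterion, however, is stated in the protocol, and in a form that admits the wrong answer.

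**The output is not binding.** A reader might infer that the trial would carry its worst dose into the pivotal study. The documents do not support that. The pattern only guides the choice, Section 1.0 brings in safety, effectiveness and past results and leaves the sponsor free to pick any active dose, and the 2x2 tables of Section 12.1.8 would show a 30% versus 55% result plainly. The fallback to 0.3% is not a safeguard here, because it deals with effective doses that cannot be told apart and not with reversed direction.

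**The size can be overstated.** A reader might count every trial in which the winning contrast is negative, which gives about 50% when all arms are equal and about 41% for 50/65/65/50. Those counts include reversed wins of patterns 1 to 3, which name no apex. A false apex with z below -1.96 occurs in only about 1% of trials for 50/60/65/65 and for 50/70/70/70, and about 3% when all arms are equal. It is more frequent where 0.4% truly falls back to control.

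**Conclusion.** The rule is wrong as written. It ranks directional patterns by a statistic whose sign it leaves open, and in chi-square form it can name arm III or IV as the apex because that arm is the worst. Only these two arms can be a false apex, since no pattern has its apex at II.

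The size depends on success rates that the protocol does not give: about 1% under a clear monotone benefit, 8% to 10% when all doses beat control by a moderate margin, and 31% to 36% when 0.4% falls back to control level. Pattern 4 itself allows for lower performance at 0.4% than at 0.3%, so a fall-off is a case that the plan has in view. The worked examples hold under all three coefficient sets. The shares in the table are for the coefficients listed.

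The harm is a pre-specified rule that can mislead and would have to be overridden to avoid the worst arm. It is not a binding selection of a wrong dose.

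**What to change.** In Section 12.1.10:
- Rank the patterns by the signed Wald z, the contrast estimate divided by its standard error, with coefficients oriented so that a positive value means the stated pattern.
- Make any pattern with z of 0 or less ineligible to guide selection.
- Print the five coefficient rows next to the patterns, against one reconciled arm numbering.
- State a 'no pattern selected' outcome for when all five z values are non-positive. This would arise in about 15% of trials if every arm had 50% success.

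With simple apex contrasts a positive z means that the arm's log-odds exceeds the mean of the other three, so the sole worst arm cannot be named. The simulated rate falls to 0%. With the umbrella-shaped apex, ranking by signed z leaves at most 0.7%.

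The cost is one or two sentences and a small table, with no new data or subjects.

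### The dose-selection rule in 12.1.10 ranks five patterns with no reference value, so it names a best fit in essentially every trial, including trials with no dose-response

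*Protocol*

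**What the plan says.** The Study Summary (Dose Selection Overview) gives the purpose: "The goal of the feasibility study is to identify either the 0.1%, 0.3% or 0.4% active dose" for comparison with control in a pivotal study. It adds that safety and past results count too, and that the sponsor may take any of the three active doses forward.

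Section 12.1.10 bases dose selection on the primary composite. It will fit a logistic regression and "apply linear contrasts to the model according to the following five dose response patterns for success". In short, the candidates are:

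1. success rising steadily across the four arms;
2. a plateau reached at 0.1% (arm II);
3. a plateau reached at 0.3% (arm III);
4. a peak at 0.3%, all other arms lower;
5. a peak at 0.4% (arm IV), all other arms lower.

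The decision rule is a plain maximum: "pattern that corresponds to the largest value of the Wald statistic will be considered the best fit and guide the selection". One supplement covers patterns that cannot separate the active arms. In its words, given "insufficient data to distinguish between effective doses, patterns 2 and 3 for example, the 0.3% rh-bFGF dose may be selected"; the grounds it names are earlier data and pre-clinical work.

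The section gives no contrast coefficients and does not say whether the Wald statistic is a signed z or a chi-square. The protocol states no expected success rate for the composite.

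**The concern.** All five patterns describe some active dose doing better than control. A largest value always exists, and here it need not exceed anything. The rule therefore has no way to say that the composite showed no dose-response, and its output looks the same whether it comes from a real gradient or from sampling noise.

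The sole primary objective (4.1.1) is to obtain dosing data and help guide the dose for a future study. Section 12.1.2 already concedes that testing on the primary endpoint is not expected to be conclusive. A named best-fit pattern, reported without any measure of how easily chance produces it, could be read as evidence from this trial when it is not.

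This is not a gap that an SAP would ordinarily fill. Coefficients may be left to an SAP, but the candidate set and the decision rule are fixed in the protocol.

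**Working it through.** **The plan's own figures.** No operating characteristic is stated for the dose rule, but the sample size it would run on can be checked (12.1.2). For LBG the standard error is √(1.20²/20 + 2.30²/20) = √0.3365 = 0.580, and 1.70/0.580 = 2.93. With 28.6 Satterthwaite degrees of freedom and two-sided 5%, power is 80.8%, which agrees with the stated 80%. Also 80/0.85 = 94.1, against 94 randomized. The working size is therefore 20 evaluable per arm, allocated 1:1:1:1.

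**Assumptions.** These are needed because the protocol is silent:
- Common true success rate of 10%, 30%, 50% or 70%.
- Contrasts over arms I-IV: pattern 1 (-3,-1,1,3) or actual-dose spacing; pattern 2 (-3,1,1,1); pattern 3 (-1,-1,1,1) or (-5,-1,3,3); pattern 4 (-1,-1,3,-1), or the umbrella forms (-3,1,5,-3) and (-1,0,1,0); pattern 5 (-1,-1,-1,3).
- Wald statistic taken both as signed z and as chi-square.

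**Formula.** With x successes of 20 in an arm, L = ln[(x+0.5)/(20.5-x)] and V = 1/(x+0.5) + 1/(20.5-x). For each pattern z = Σ cL / √(Σ c²V). The largest z (or z²) wins.

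**An example by hand.** Take counts of 10, 10, 11 and 10, so that the arms differ by one success. Then L = ln(11.5/9.5) = 0.191 for arm III and 0 elsewhere; V = 0.192 for arm III and 0.190 elsewhere.

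| Pattern | z |
|---|---|
| 1 | 0.191/1.952 = 0.10 |
| 2 | 0.191/1.512 = 0.13 |
| 3 | 0.191/0.874 = 0.22 |
| 4 | 0.573/1.517 = 0.38 |
| 5 | -0.191/1.512 = -0.13 |

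Pattern 4 is the best fit at z = 0.38. With counts 10, 10, 9 and 10 every sign flips. The chi-square form still gives pattern 4 the largest value (0.38² = 0.14), so it names an apex at the arm that did worst.

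**All outcomes.** Enumerating all 21⁴ outcomes with one common true rate gives:

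| Quantity under no effect | Result |
|---|---|
| All statistics zero, so no pattern named | 0.3-0.4% at rates 30-70%; 1.4% at 10% |
| Patterns 2+3+4 win | 49-70% over the codings examined |
| of which simple step/apex coding | 61-67% signed; 69-70% chi-square |
| Patterns 3+4 only | 32-46% |
| Patterns 1+5 | 30-51% |
| Chi-square form: winner has the wrong sign | about 45-52% |

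The shares are illustrations and not bounds; other pairings of these codings move them by a few points.

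Fixing the sign alone is not enough. At rates of 30-70% with simple codings, all five signed contrasts are negative in only about 14-16% of no-effect trials, so in about 85% a positive contrast produced by chance still wins.

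**Reference value.** Under no effect at rates of 30-70% with simple codings, the 95th percentile of the largest signed z is about 2.0-2.1. A cut-off of 1.645, unadjusted for five contrasts, is passed in 12-14% of trials; 2.1 is passed in about 5% or less.

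**How often 2.1 is passed when there is an effect** (control 40%, first coding, over the pattern shapes):

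| Best arms | Passed |
|---|---|
| 80% | about 80-96% |
| 70% | about 55-78% |
| 60% | about 30-46% |

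**The case against.** Any best-of-k rule names a winner, and the stated goal is to select a dose for a pivotal trial, where effect will be shown against control. Ranking is a legitimate tool for that. The decision is also not mechanical: the pattern only guides, safety and past results count, the sponsor may choose any active dose, and the study is not for labeling. All of this stands, and it lowers the severity. None of it tells a reader how far the named pattern differs from chance.

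Two stronger readings are tempting and are not supported.

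- A reader might infer that the rule steers about two thirds of no-effect trials to 0.3%. That share depends on coefficients and a form of the Wald statistic that the protocol does not state. It also counts every pattern 2 win as 0.3%, although the text only permits that choice. Without that optional default the share is 32-46% in the codings examined, against one third if three doses were drawn at random.
- A reader might infer that the trial cannot report absence of effect. It can: 12.1.8 compares each dose with control on the same composite, and 12.1.9 does so for LBG and ΔCAL, with LBG powered at 80%. The defect is confined to 12.1.10, which does not refer to those results.

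It is also fair to object that a hard significance gate would cost too much. At 40% versus 60% success most trials would fail it, and a selection study should not discard its ranking for that reason.

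**Conclusion.** The point holds for 12.1.10 taken on its own terms. That a pattern is named in essentially every no-effect trial follows from the rule's construction and needs no assumption beyond how exact ties are counted. The wrong-sign result, about half of no-effect trials, applies only if the statistic is read as chi-square, which the text does not exclude. The shares by pattern rest on assumed codings, 20 per arm and equal true rates, and should be quoted only as ranges.

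The result of 12.1.10, as written, is not evidence that any dose works on the composite. Because the rule guides without binding, and because separate control comparisons exist, the severity is minor to moderate.

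**What to change.** Amend 12.1.10 as follows:

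- Define each contrast so that a positive value means active better than control, and rank the signed statistics.
- Beside the best-ranking pattern, report a one-sided p-value for the largest of the five. Take it from the null distribution obtained by permuting arm labels within smoking stratum and recomputing all five contrasts each time, so that it is adjusted for the choice among them.
- If that p-value exceeds 5%, still report the best-ranking pattern. State that a dose-response on the composite was not shown, and that any dose taken forward rests on prior data, safety and the other endpoints.
- Do not use the cut-off to suppress the pattern or to restrict the sponsor's choice.

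The cost is a few sentences and a short permutation program, with no change to sample size or conduct. The downside should be stated in the plan: for modest real effects a not-shown result will be common. At control 40% and best arms 60%, only about 30-46% of trials pass a 2.1 cut-off. The wording should therefore make clear that not shown does not mean absent.

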12.1.11 Safety Analysis

All AEs will be coded according to the Medical Dictionary for Regulatory Activities (MedDRA) and additional pre-specified codes for device-specific local AEs or classified using a pre-specified ordinal scale. The classes of AEs will be summarized by type (by organ class and preferred term), incidence, timing (intra-operative, post-operative), severity, and relationship to study treatment for each treatment group; event counts will also be summarized by system organ class and preferred term. All AEs will also be sorted into local vs. systemic events. Patients reporting multiple

episodes will be counted once under the worst severity and the strongest relationship, respectively. In addition, SAEs will be presented by relationship to study treatment.

Local events, clinical signs or symptoms, rh-bFGF antibody above baseline, and delayed healing will also be assessed. The subject-level incidence of these outcomes will be analyzed using a two-sided Fisher Exact test while the event-level incidence will be analyzed using a Wilcoxon test.

Safety analyses will be performed on the ITT population receiving any study treatment.

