9.1.2 Additional Points to Consider for AEs

An untoward finding generally may:

- Indicate a new diagnosis or unexpected worsening of pre-existing condition of periodontitis. (Intermittent events for pre-existing conditions underlying disease should not be considered AEs.)
- Necessitate unexpected surgical intervention and/or medication.
- Be considered unfavorable by the Investigator for any reason.

Diagnoses vs. signs and symptoms:

- Each event should be recorded to represent a single diagnosis. Accompanying signs or symptoms should NOT be recorded as additional AEs. If a diagnosis is unknown, sign(s) or symptom(s) should be recorded appropriately as an AE(s).

Worsening or changes in severity of AEs:

- If the subject experiences a worsening or complication of an AE after any change, the worsening or complication should be recorded as a change to an existing AE.
- If the subject experiences changes in severity of an AE, the event should be captured once with the maximum severity recorded.

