9.1.3 Expected AEs

Following the periodontal flap procedure, pain, swelling, soreness, erythema, edema, bleeding and temporary numbness are expected to occur 80% to 100% of the time. These sequelae are related to the surgical procedure, not the product and typically resolve over time as the wound heals. Occasionally (less than 5% of the time), fever, pus and infection of the surgical site may occur as post-surgical adverse events.

In addition, headaches, tooth pain and tooth disorder (less than 10%) were reported as AEs related to periodontal grafting procedures in the summary of effectiveness and safety data for a similar product (GEM 21S TM).

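### For the surgical reactions expected in 80 to 100% of subjects, the planned Fisher test on incidence is at a ceiling, and neither planned test measures their severity or duration

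*Protocol*

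**What the plan says.** Protocol 12.1.11 lists the outcomes: "Local events, clinical signs or symptoms, rh-bFGF antibody above baseline, and delayed healing will also be assessed". It then fixes two tests. The first is "The subject-level incidence of these outcomes will be analyzed using a two-sided Fisher Exact test"; the second is that "the event-level incidence will be analyzed using a Wilcoxon test". The same section summarises adverse events by severity, timing and relationship for each arm, counting each patient once at worst severity, but attaches no test to that summary.

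Protocol 9.1.3 gives background rates after the flap procedure. On the common reactions: "pain, swelling, soreness, erythema, edema, bleeding and temporary numbness are expected to occur 80% to 100% of the time". It attributes these to the surgery and not to the product. On others: "Occasionally (less than 5% of the time), fever, pus and infection of the surgical site may occur".

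Under 9.1.2, when an event changes in severity, "the event should be captured once with the maximum severity recorded". Worsening is an update to the existing record, and signs that accompany a diagnosis are not separate events. Severity is graded mild, moderate or severe (9.1.6), and start and stop dates are recorded (9.2.1.2).

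The Study Summary says that a dose will be identified "based on the observed safety and effectiveness together with past study results".

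**The concern.** All four arms have the same flap surgery, so all four start at the same high rate of these reactions. A harmful dose would be expected to make swelling or pain worse or longer, not to turn a rare event into a common one. A yes/no test cannot register that kind of change. The count-based test is blind to it as well, since a more severe or longer episode is still one record. The study has to help choose a dose, partly on safety. A non-significant Fisher result on near-universal events could be read as reassurance that the doses are alike locally, when the test had little chance of saying anything else.

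**Working it through.** **Inputs.** 94 randomised, 80 evaluable, 1:1:1:1 allocation (5.1, 12.1.2): 94/4 = 23.5, taken as 23 per arm, and 80/4 = 20 per arm. Background 80 to 100% (9.1.3), read as applying to each listed reaction. Two-sided alpha of 0.05 is an assumption for safety, because 12.1.1 states it for effectiveness endpoints only.

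**The plan's own power figure.** No power is stated for any safety comparison. The one stated figure, at least 80% for linear bone growth with 20 per arm, reproduces. SE = √[(1.20² + 2.30²)/20] = √0.3365 = 0.580; 1.70/0.580 = 2.93; Satterthwaite df = 28.6; power = 80.8%.

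**Fisher at the ceiling.** Take the most extreme case, with all n subjects on a dose affected.

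- n = 20: 15/20 on control gives p = 2·C(20,5)/C(40,5) = 2 × 15,504/658,008 = 0.047. 16/20 gives 0.106. So control must be at 15/20 = 75% or lower.
- n = 23: 18/23 on control gives p = 2·C(23,5)/C(46,5) = 2 × 33,649/1,370,754 = 0.049. 19/23 gives 0.109. So control must be at 18/23 = 78% or lower.

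Both cut-offs lie below the range the protocol expects. Power is the chance that control falls that low by luck: P(X ≤ 15) for X ~ Bin(20, π), or P(X ≤ 18) for X ~ Bin(23, π).

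| Background π | n = 20 | n = 23 |
|---|---|---|
| 80% | 37% | 50% |
| 85% | 17% | 26% |
| 90% | 4% | 7% |
| 95% | 0.3% | 0.5% |
| 100% | 0 | 0 |

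These are upper limits. With 20 per arm, 80% against 95% gives 17%.

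**Event counts.** Counts have no ceiling of their own. If events per subject were Poisson (assumed), the Wilcoxon test with 20 per arm would have 36% power for means of 3 v 4 and 85% for 3 v 5. That is power for more events, not for worse or longer ones: a subject whose single swelling record moves from mild to severe contributes the same count.

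**What a severity comparison could add.** The documents give no severity distribution, so this is illustration only. Control none/mild/moderate/severe is assumed to be 10/55/30/5% (A) or 20/45/30/5% (B), with a proportional-odds shift on one dose, 23 per arm, 4,000 simulated trials per row, and a tie-corrected Wilcoxon test in place of its exact form.

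| Odds ratio | A: worst severity, Wilcoxon | A: incidence, Fisher | B: worst severity, Wilcoxon | B: incidence, Fisher |
|---|---|---|---|---|
| 1 (null) | 5% | 2% | 5% | 3% |
| 2 | 21% | 2% | 23% | 7% |
| 3 | 47% | 3% | 51% | 14% |
| 4 | 67% | 4% | 69% | 18% |

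In a different scenario, incidence stays at 90% in both arms and only severity moves, from 10/60/25/5% to 10/30/35/25%, with 20 per arm. The rank test has about 45% power and Fisher on incidence rejects in about 1% of trials.

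**The case against.** The strongest reply is that the plan does look at graded local harm. Severity is tabulated by arm at each patient's worst grade. The 0 to 4 wound-healing scale and the gingival wound evaluation at 2 and 4 weeks are compared among treatments (4.2.2, 5.2.3). This stands, so it would be wrong to infer that the arms are compared on local effects only by the two tests in 12.1.11. It leaves a gap, though. The wound-healing scale is an effectiveness endpoint at two visits; it grades redness, edema and bleeding but not pain, soreness, numbness or how long an event lasted.

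A reader might also infer that all local events are at a ceiling. The documents do not support that. Fever, pus and infection are expected in fewer than 5%, and no high background is stated for delayed healing or antibody rise. With 20 per arm, Fisher has 72% power for 5% v 40% and 89% for 5% v 50%, so it remains a reasonable choice there.

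It can be said, too, that this is a feasibility study with tests for internal use (12.1.1), that 12.1.10 bases dose selection on the primary composite, and that no rule makes a safety p-value decisive. All true, and this limits the weight of the point. That safety test details may be left to an analysis plan is a weaker reply, because the protocol itself names the tests here.

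Finally, the four arms are ordered doses, and one might conclude that a trend test is required. It is not: 12.1.10 treats plateau and apex patterns as plausible for effectiveness, so a monotone effect cannot be presumed.

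**Conclusion.** The point holds for the seven reactions named in 9.1.3. For them, the protocol's own rates make any-event incidence a nearly uninformative test variable: power is at most 50% (23 per arm) or 37% (20 per arm) in the most extreme case, and 7% or 4% at most once the background reaches 90%. The event-level test does not fill the gap, and the severity already collected is described but not tested. The Fisher figures rest only on the documents, an alpha of 0.05, and reading the 80 to 100% as the rate of each reaction. If it means having any of them, single reactions could be less common and less close to the ceiling.

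Two stronger readings are not supported. Local harm would not go unseen, since the severity table and the wound-healing comparisons remain. Nor would a severity test be well powered in general: about one in five at an odds ratio of 2, and about two in three only at 4, under an assumed severity mix. This is a moderate weakness worth correcting, not a flaw that undermines the study.

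**What to change.** In 12.1.11, for the reactions that 9.1.3 expects after the flap procedure, compare each dose with control by an exact Wilcoxon test on (a) each subject's worst severity, ordered none, mild, moderate, severe, and (b) duration from the recorded start and stop dates, with zero for subjects without the event and a stated rule for events still ongoing at the last visit. An ordered-dose trend test may be added as supportive. Keep Fisher's exact test for uncommon outcomes: serious adverse events, infection, pus, fever, antibody rise and delayed healing. State that a non-significant incidence test on the expected reactions is not evidence that the doses are alike.

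The cost is a few lines of text, one extra table and some additional exploratory tests. No new data are needed, and the sample size does not change. A trend test loses power if the effect is not monotone, so the comparisons with control should remain the main ones.
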